Revised exclusion criteria to enhance enrollment (#5), to provide a definition for “as needed” (pro re nata [PRN]) use (#6), to provide comprehensive list of exclusionary medications (#6), to clarify “hyperthyroidism/or hypothyroidism” (#8), and to remove history of serious allergic reactions (such as anaphylaxis) as this is not included in the approved drug labeling (#11)	Section 4.2.2 Exclusion Criteria (#5, #6, #8, #11)
Clarified procedures to follow if emergency unblinding is required	Section 5.5.2 Emergency Unblinding
Added collection of menstrual cycle data in the study to facilitate meaningful analysis of reproductive hormone data	Table 1 Schedule of Events (row added; new footnote #6 added)
Clarified the visits (days on which blood samples are not collected) when study drug may be administered prior to study assessments to provide more flexibility in drug administration.	Table 1 Schedule of Events (footnote #7)
Added collection of a laboratory sample for hepatitis B surface antigen and hepatitis C antibody at the end-of-study visit	Table 1 Schedule of Events Section 7.6.4.3 Laboratory Testing
Removed the requirement that patients be identified by their initials on case report forms (CRFs) and other documents submitted to the sponsor to preserve patient confidentiality	Section 13.3 Patient Confidentiality and Data Protection
Removed gabapentin from the list of exclusionary medications since use of gabapentin won’t impact interpretation of study endpoints	Appendix 3 Mood Stabilizers, Antipsychotics, and Medications to Treat Dementia
Provided a more comprehensive list of medications for calculating the anticholinergic burden (ACB)	Appendix 4 Drugs on the Anticholinergic Burden Scale
Made minor editorial changes	Table 1 Schedule of Events

Amendment 3

The main purpose of this amendment is to incorporate the following changes requested during the regulatory review via the Voluntary Harmonization Procedure (VHP).

- To add a history of serious allergic reactions and severe hepatic impairment as exclusion criteria.
- To provide the list of highly effective contraception methods in accordance with recommendations of the Clinical Trial Facilitation Group (CTFG).
- To describe the procedure to be followed if emergency unblinding of a patient by the investigator is required during the study.

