4.2.1. Inclusion Criteria

A patient must meet the following criteria to be eligible for inclusion in the study:

1. Men and women \geq age 40 and \leq age 85
2. Patients with heFH (see [Appendix 1](#) and [Appendix 2](#) for diagnosis criteria) or non-FH patients at high or very high cardiovascular risk

High and very high cardiovascular risk patients include patients with coronary heart disease (CHD), non-CHD CVD, and other risk factors. Definitions for CHD, non-CHD CVD, and other risk factors:

- a. A documented history of CHD (includes 1 or more of the following):
 - i. Acute myocardial infarction
 - ii. Silent myocardial infarction
 - iii. Unstable angina
 - iv. Coronary revascularization procedure (eg, percutaneous coronary intervention or coronary artery bypass graft surgery)
 - v. Clinically significant CHD diagnosed by invasive or non-invasive testing (eg, coronary angiography, stress test using treadmill, stress echocardiography, coronary calcium scan, or nuclear imaging).
- b. Non-CHD CVD (includes 1 or more of the following criteria):
 - vi. Documented previous ischemic stroke with a focal ischemic neurological deficit that persisted more than 24 hours, considered as being of atherothrombotic origin. Computed tomography (CT) or magnetic resonance

imaging (MRI) must have been performed to rule out hemorrhage and non-ischemic neurological disease.

- vii. Peripheral arterial disease
- viii. Abdominal aortic aneurysm
- ix. Atherosclerotic renal artery stenosis
- x. Carotid artery disease (transient ischemic attacks or >50% obstruction of a carotid artery)

c. Other risk factors

- xi. Documented moderate chronic kidney disease as defined by $30 \leq$ Estimated Glomerular Filtration Rate (eGFR) <60 mL/min/1.73 m² for 3 months or more, including the screening visit
- xii. Type 1 or type 2 diabetes mellitus
- xiii. A calculated 10-year fatal CVD risk SCORE $\geq 5\%$ (ESC/EAS Guidelines for the management of dyslipidemias, [Perk 2012](#))

* For CVD risk categories, see [Appendix 5](#).

3. Patients with history of CHD not having adequate control of their hypercholesterolemia with LDL-C ≥ 70 mg/dL, or all other patients with LDL-C ≥ 100 mg/dL

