12. Pregnant or breastfeeding women

13. Women of childbearing potential* who are unwilling to practice highly effective contraception prior to the initial dose/start of the first treatment, during the study, and for at least 6 months after the last dose. Highly effective contraceptive measures include stable use of combined (estrogen and progestogen containing) hormonal contraception (oral, intravaginal, transdermal) or progestogen-only hormonal contraception (oral, injectable, implantable) associated with inhibition of ovulation initiated 2 or more menstrual cycles prior to screening; intrauterine device (IUD); intrauterine hormone-releasing system (IUS); bilateral tubal ligation; vasectomized partner; and/or sexual abstinence**.

*Postmenopausal women must be amenorrheic for at least 12 months in order not to be considered of childbearing potential. Pregnancy testing and contraception are not required for women with documented hysterectomy or tubal ligation.

**Sexual abstinence is considered a highly effective method only if defined as refraining from heterosexual intercourse during the entire period of risk associated with the study treatments. The reliability of sexual abstinence needs to be evaluated in relation to the duration of the clinical trial and the preferred and usual lifestyle of the subject.

14. A positive human immunodeficiency virus (HIV) test
15. Patients with severe hepatic impairment (Child-Pugh Class C)

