Research samples (serum and plasma)			X			X		X				X	
			X										

ADA = anti-drug antibody, CPK = creatine phosphokinase, EOS = end of study, F/U = follow-up, HbA1c = hemoglobin A1c, hs-CRP = high-sensitivity

C-reactive protein, S = serum, TSH = thyroid-stimulating hormone, U = urine, WOCBP = women of childbearing potential

- Visit 2 is optional.
- Injection training will be performed with the patient and/or caregiver at visit 2, at visit 3, or at visits 2 and 3 using placebo. Refer to Section 5.1 for additional information on injection training.
- The patient or caregiver will administer the first dose of double-blind study drug in the clinic on day 1. The patient will be monitored for 30 minutes after the first dose. Subsequent doses of study drug must be administered Q2W. Study drug will be administered at home between week 84 and week 94. The last dose of study drug will be administered at home at week 94. Patients will come into the clinic for the last study visit at week 96.
- Injection supplies and the dosing log will be provided to the patient.
- See Appendix 6 for diet.
- Menstrual cycle data will be collected for women of childbearing potential who are not on hormonal contraceptives.

7. On days when a clinic visit coincides with a dosing day (visits 3, and 8), blood samples (including ADA samples) will be collected after study assessments are performed and before the dose of study drug is administered. At visits 4, 5, 6, 7, 9, 10, and 11, study drug may be administered prior to study assessments.
8. If a neurocognitive AE is reported during the visits when the test is not planned or in case of early treatment discontinuation, an unscheduled neurocognitive battery test will be performed.
9. Samples will be tested for Total-C, calculated LDL-C, HDL-C, TG, and non-HDL-C, Apo B, Apo A-1, Apo B/Apo A-1 ratio, and Lp(a).
10. For female patients – estradiol, follicle-stimulating hormone (FSH) and luteinizing hormone (LH); for male patients – testosterone, FSH and LH.
11. Dipstick and, if abnormal, microscopy.

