5.8. Analysis of Other Variables

The summary of other variables will be presented by treatment groups (Praluent, placebo) on the safety population. No formal inferential testing will be performed for either period. Summaries will be descriptive in nature.

All measurements, scheduled or unscheduled, fasting or not fasting, will be assigned to analysis windows in order to provide an assessment for week 8 to week 96 time points.

Hs-CRP and HbA1c parameters (Section 4.8) will be summarized by treatment group for the number of patients with data, mean, SD, median, minimum, and maximum (for hs-CRP, Q1 and Q3 will be also provided) by analysis visit during the treatment period. For HbA1c, summaries will also be provided according to diabetes mellitus status at baseline. The time profile will be plotted by treatment group for HbA1c showing the means and the corresponding SEs, while medians (with Q1-Q3) will be plotted for hs-CRP. Applying the PCSA criteria to these variables at any time during the TEAE period, the number of patients (and percentages) meeting the criteria will be summarized by treatment group.

The gonadal hormone parameters (Section 4.8) will be summarized by treatment group for the number of patients with data, mean, SD, median, minimum, and maximum by analysis visit during the treatment period. For FSH and LH, the summaries will be performed for all patients, female patients, and male patients. Estradiol will be summarized for female patients only, and testosterone will be summarized for male patients only. Summary tables will also be provided for gonadal hormone parameters based on measurements outside the central laboratory normal ranges, if applicable.

In order to minimize confounding factors with menopause or exogenous estrogens, the summaries of estradiol, FSH, and LH for female patients will be repeated by excluding patients who were receiving hormone replacement therapy, were ≥ 50 years, or had FSH levels ≥ 25 IU/L at baseline.

For male patients, the summaries of testosterone, FSH, and LH will be repeated by excluding patients who were receiving testosterone supplementation or had LH levels ≥ 15 IU/L at baseline.

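### SAP 5.8: the restricted female hormone summary is meant to limit exogenous estrogens but keeps hormonal-contraceptive users, so any difference is diluted and a null result reassures little

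*SAP*

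**What the plan says.** **The planned summaries.** SAP Section 5.8 summarizes the gonadal hormones descriptively, by treatment group and analysis visit, with no formal testing. It then repeats the female estradiol, FSH and LH summaries on a restricted set, with this purpose: "In order to minimize confounding factors with menopause or exogenous estrogens". The repeat summaries "will be repeated by excluding patients who were receiving hormone replacement therapy". Women aged 50 or over are also left out, as are those who "had FSH levels ≥ 25 IU/L at baseline". Hormonal contraceptives are not mentioned. The parallel rule for men leaves out those on testosterone supplementation or with baseline LH of 15 IU/L or more.

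**Who can be in the restricted set.** Protocol Section 4.2.1 sets the lower age limit at 40. For women of childbearing potential, exclusion criterion 13 (Section 4.2.2) states: "Highly effective contraceptive measures include stable use of combined (estrogen and progestogen containing) hormonal contraception". It also accepts "progestogen-only hormonal contraception (oral, injectable, implantable) associated with inhibition of ovulation", together with several non-hormonal methods.

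**Menstrual-cycle data.** Protocol Table 1, footnote 6, reads: "Menstrual cycle data will be collected for women of childbearing potential who are not on hormonal contraceptives". The table schedules this at screening, baseline and weeks 24, 48, 72 and 96, which are the visits with gonadal hormone samples. The amendment history gives the reason: "Added collection of menstrual cycle data in the study to facilitate meaningful analysis of reproductive hormone data". The readable SAP states no use for these data. Its nearest item is menopausal status, listed among the baseline characteristics in Section 4.1.

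**The concern.** The stated purpose and the exclusion list do not match. A combined contraceptive is an estrogen taken as medication, so a rule meant to limit that source of confounding should deal with it. The age and FSH conditions select the women in whom contraceptive use is most plausible, and neither is designed to detect it.

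Gonadal hormones are a listed endpoint (Protocol Section 6.2.4). The all-female summary pools women up to age 85, so among the planned tables the restricted one is best placed to show an effect on ovarian hormones before menopause. If part of that set has hormone levels governed by a contraceptive, a true difference between arms is averaged with women in whom it may not appear. The practical risk is that similar means in the two arms are read as reassurance when the table had limited ability to show anything else.

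**Working it through.** The plan gives no figure for this subset, so there is nothing to reproduce. The main check is a comparison of texts. The arithmetic after it only illustrates size.

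**Step 1. Aim against rule.**

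| Source of confounding named in SAP 5.8 | Exclusion that addresses it |
|---|---|
| Menopause | Age 50 or over; baseline FSH 25 IU/L or more |
| Estrogens taken as replacement therapy | Hormone replacement therapy |
| Estrogens taken as contraception (accepted by criterion 13) | None |

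Entry from age 40 combined with the under-50 condition leaves women aged 40 to 49 with baseline FSH below 25 IU/L. Contraceptive users pass the age condition, and an upper limit on FSH would not be expected to remove them. For men, the corresponding rule does remove the exogenous hormone.

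**Step 2. Dilution.** Let c be the share of users in the subset. Assume users show no drug effect on these hormones, c is equal in both arms, and the SD is unchanged. The share of the between-arm mean difference that remains is 1 − c. Precision equal to that of an uncontaminated set needs 1/(1 − c)² times the patients. The documents do not give c.

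| Assumed c | Difference remaining | Multiple of patients |
|---|---|---|
| 10% | 90% | 1/0.90² = 1.23 |
| 30% | 70% | 1/0.70² = 2.04 |
| 50% | 50% | 1/0.50² = 4.0 |

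**Step 3. Noise from pooled cycle phases.** Let v be the share of variance due to cycle phase, also not in the documents. Ignoring phase inflates the standard error by 1/√(1 − v): 1.15 at v = 25%, 1.41 at 50% and 2.0 at 75%.

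**Step 4. Does excluding users cost more than it gains?** Assume 40 women per arm. As a yardstick only, since no test is planned, take the difference detectable with 80% power at two-sided 5%: (1.960 + 0.842) × √(2/40) = 0.63 SD with no users in the set.

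- With 30% users kept, the effect in non-users must be 0.63/0.70, about 0.89 SD.
- With those users excluded, 28 per arm remain: 2.802 × √(2/28) = 0.75 SD.

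Under these assumptions exclusion is better despite the smaller number. The yardstick grows by 1/√(1 − c) instead of 1/(1 − c).

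**Step 5. How small the subset may be.** Assume 40% of patients are women and 10% of those fall in the restricted set: 1085 × 0.40 × 0.10 = 43 per arm. With 20% to 40% users, 9 to 17 of the 43 are users and 26 to 34 remain. Two cycle-phase bands would hold about 13 to 17 each. With the planned retention of 0.80 × 0.75 = 0.60, that is about 8 to 10 per band and arm at week 96.

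**The case against.** Several points on the other side stand.

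- **The table still has value.** A reader might infer that it cannot show an effect on ovarian hormones at all. The documents do not support that. Allocation is randomized 1:1 and blinded, so contraceptive use and cycle phase are balanced in expectation. The result is dilution and noise.
- **A false signal is not the main risk.** A reader might infer that an uneven share of users would pass for a drug effect. Chance imbalance is possible in a small subset, since the strata are age (under 65, or 65 and over) and statin use. But criterion 13 requires stable use begun before screening. SAP Section 5.1 places other baseline safety data alongside the post-baseline data, so where that is applied to these tables an imbalance at entry would show. Concomitant medications are tabulated by arm, though not within this subset.
- **No protocol promise is broken.** A reader might infer that the SAP discards data it was bound to analyze. Protocol Section 9.5.2.10 asks only for summaries by time point, and the amendment history gives a reason for collection without committing to a cycle-phase analysis. Text is redacted after SAP Section 5.9 and after Protocol Section 7.6.6.2, so use of the cycle data there cannot be ruled out.
- **The subset is mixed.** Criterion 13 also lists non-hormonal methods, and women under 50 with low FSH are not all cycling. Progestogen-only products are not estrogens, so strictly only combined products defeat the stated aim.
- **The stakes are limited.** These are other endpoints, described without testing.

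None of this removes the mismatch between the stated aim and the exclusion list. Hormone replacement therapy might be programmed to cover contraceptives, but the SAP does not say so.

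**Conclusion.** The point holds in a limited form. As written, the restricted female summary does not meet its stated aim, because permitted hormonal-contraceptive users, including users of estrogen-containing products, stay in it. Any treatment difference is diluted and noisier, and an absence of difference is weak reassurance.

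The size cannot be fixed from the documents. Across assumed user shares of 10% to 50%, between 90% and 50% of a difference would remain, provided users show no drug effect. The noise figures rest on an assumed variance share for cycle phase.

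The primary noninferiority test and the lipid and adverse-event analyses are untouched. This is a small, specific correction to one descriptive table. A compulsory breakdown by cycle phase does not follow from it, given how few women each cell might hold.

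**What to change.** In SAP Section 5.8, extend the exclusions for the restricted female summary to women using hormonal contraceptives at baseline or during the treatment period, or show these women in a separate row. Identify them from the medication records, which SAP Section 4.3 already has collected and coded with WHO-DD. State the number of women per arm at each visit.

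Where numbers allow, add an optional supportive display of the remaining women's values by cycle timing, using the menstrual-cycle data. If the cells are too small, a listing is enough. The readable text does not say which menstrual items are recorded, so the timing variable must be defined from the case report form.

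The cost is a wording change, one derived flag and a smaller subset. No new data collection is needed, and the change can be made before database lock.

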2.3. Study Plan

The study consists of the following 2 periods, which are shown schematically in [Figure 1](#).

- A screening period of up to 3 weeks.

The patient or caregiver will be trained to self-inject/inject using a dose of placebo during the screening period or at the first visit of the double-blind treatment period.

- A double-blind treatment period of 96 weeks.

On day 1 (baseline), after completion of study assessments and after collection of blood samples, and as soon as possible after the patient is randomized into the study, the first dose of study drug will be administered. The patient will be

monitored at the clinical site for 30 minutes after the first dose. Subsequent doses of study drug must be administered Q2W. The last dose of study drug will be administered at week 94.

[figure not shown]
Patients' neurocognitive function will be assessed every 6 months.

The dose of study drug will be increased (using a blinded process) at the week 12 visit in patients whose LDL-C levels are ≥ 50 mg/dL (1.3 mmol/L) at week 8. Those patients who are randomized to Praluent will receive Praluent 150 mg Q2W at week 12 and until end of study. All patients randomized to placebo will continue to receive placebo.

Lipid results will be blinded for specimens obtained after randomization. No attempts should be made by the investigator or patient to have the patient's lipid values evaluated independently from the time of randomization until the last study visit.

Patients should be on a stable regimen of lipid-modifying therapy (LMT) (including a maximally-tolerated dose of statin, unless statin-intolerant) for 28 days prior to screening, as well as on a stable diet. Patients will be asked to maintain both their statin dose and diet from screening to the end of the study.

Figure 1: Study Flow Diagram

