4.7.1. Adverse Events Variables

The period of safety observation starts from the time when the patient gives informed consent and continues into the following periods:

- The PRE-TREATMENT period: defined as the time from the signed informed consent up to the first study treatment injection.
- The treatment-emergent adverse event (TEAE) period: defined as the time from the first study treatment injection up to the day of the last study treatment injection + 70 days (10 weeks), as residual effect of Praluent is expected until 10 weeks after last dose of study treatment.

The TEAE period will include:

- The TREATMENT period is defined as the time from the first study treatment injection up to the day of last study treatment injection + 21 days, as serum concentration of alirocumab >10 µg/mL is expected for approximately 21 days following administration of 150 mg. Further, in previous studies, alirocumab concentrations declining below this concentration also showed a decrease in effect on LDL-C.
- The RESIDUAL TREATMENT period is defined as the time from the day of last study treatment injection + 22 days up to the day of last study treatment injection + 70 days (10 weeks).
- The POST-TREATMENT period: defined as starting the day after the end of the TEAE periods (i.e., 71 days after the last study treatment injection) up to the patient's end of study.

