4.8. Other Variables

Other assessment endpoints are listed and defined below. Protocol schedule visits will be assigned to the Analysis Windows (See Appendix 10.2).

- The percent change in hs-CRP from baseline to protocol specified visits. Hs-CRP values greater or equal to 10 mg/L will be excluded from analyses in a second approach, since these are suggestive of concurrent infection(1). PCSA (potentially clinically significant abnormalities) criteria for hs-CRP are listed in Appendix 10.3.
- The absolute change in HbA1c (%) from baseline to protocol specified visits. PCSA criteria for HbA1c are listed in Appendix 10.3.
- The proportion of patients with two consecutive results, separated by at least 21 days, of calculated LDL-C <25 mg/dL (<0.65 mmol/L) (and again for calculated LDL-C <15 mg/dL [< 0.39 mmol/L]) during the treatment period.
- The proportion of patients with at least one result of calculated LDL-C <25 mg/dL (<0.65 mmol/L) (and again for calculated LDL-C <15 mg/dL [< 0.39 mmol/L]) during the treatment period.
- For the patients with two consecutive results as described above, the time to the first calculated LDL-C <25 mg/dL (<0.65 mmol/L) (and again for calculated LDL-C <15 mg/dL [< 0.39 mmol/L]) during the treatment period.

- Gonadal hormone levels (for female patients - estradiol, follicle-stimulating hormone (FSH) and luteinizing hormone (LH); for male patients - testosterone, FSH and LH)

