Binary endpoints defined in Section 4.8 will be described through patient counts and percentages. Kaplan-Meier curves will be provided for the variables assessing time to first occurrence of an event (i.e., calculated LDL-C related outcome). Patients not meeting the event will be censored at the end of the treatment period. For the analysis of the time to the first of the two consecutive LDL-C events, patients without post-baseline LDL-C result or with only one post-baseline LDL-C result will not be included in the analysis.

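### The Kaplan-Meier curve for confirmed very low LDL-C censors at the end of treatment, which biases it slightly low when patients stop early

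*SAP*

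**What the plan says.** SAP 4.8 lists three outcomes for very low calculated LDL-C, each for the 25 and the 15 mg/dL threshold and each limited to the treatment period:

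- a confirmed proportion: "The proportion of patients with two consecutive results, separated by at least 21 days, of calculated LDL-C <25 mg/dL";
- an unconfirmed proportion: "The proportion of patients with at least one result of calculated LDL-C <25 mg/dL";
- an event time: "For the patients with two consecutive results as described above, the time to the first calculated LDL-C <25 mg/dL".

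SAP 4.7.1 says the treatment period "is defined as the time from the first study treatment injection up to the day of last study treatment injection + 21 days".

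SAP 5.8 summarises the two proportions as counts and percentages and the event time by Kaplan-Meier. Its censoring rule is "Patients not meeting the event will be censored at the end of the treatment period". For the confirmed event it adds that "patients without post-baseline LDL-C result or with only one post-baseline LDL-C result will not be included in the analysis". The section uses the safety population and plans no formal testing.

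Protocol Table 1 draws the lipid panel after baseline at weeks 8, 12, 24, 48, 72 and 96. Protocol 7.3.1 asks for an extra visit with the end-of-study assessments when study drug is stopped, within 5 days if possible, after which the patient returns to the normal schedule. The end-of-study column of Table 1 includes lipids, and SAP 5.8 and 6.6 let unscheduled results count.

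**The concern.** A low value becomes an event only if the next on-treatment value, at least 21 days later, is also low. The last on-treatment LDL-C can therefore never be an event date. The same holds for a value followed by its only on-treatment successor less than 21 days later. Censoring at last injection + 21 days still places the patient in the risk set on such a date, so the patient is in the denominator and cannot enter the numerator.

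The SAP accepts this logic for patients with fewer than two results and excludes them. It does not apply it to the unconfirmable last values of the others. The exclusion also counts post-baseline rather than on-treatment results. Because patients who stop the drug stay on the visit schedule, someone with one on-treatment and one off-treatment result passes the exclusion although no event is possible.

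Protocol 1.1 notes that clinical data on very low circulating LDL and cognition are limited. Of the planned summaries of this outcome, the curve is the only one that allows for unequal follow-up.

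**Working it through.** **The plan's own figure.** No figure is stated for this curve. The dropout inputs appear only in the sample size (SAP 2.2): 2 × (1.960 + 1.645)² × 1.0² / 0.2² = 649.7, so 650 per group against the stated 651. Then 651 / (0.80 × 0.75) = 1085, as stated.

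**Completers.** "The last dose of study drug will be administered at week 94", which is day 1 + 94 × 7 = 659, so the treatment period ends on day 680. A first low value at week 72 (day 505) can be confirmed at week 96 (day 673). A first low value at week 96 cannot be confirmed, but no events are dated there, so staying at risk does no harm. A completer who misses the week 94 dose is an exception: last dose day 645, period ends day 666, before day 673.

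**Early stoppers, by hand.** Take 20% and 25% yearly dropout as treatment discontinuation (an assumption) with a constant hazard within each year: S(t) = 0.8^(t/52) to week 52, then 0.8 × 0.75^((t−52)/52). The share stopping between lipid visits is:

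- week 8 to 12: 1 − 0.8^(4/52) = 1.7%
- week 12 to 24: 1 − 0.8^(12/52) = 5.0%
- week 24 to 48: 1 − 0.8^(24/52) = 9.8%
- week 48 to 72: 1 − 0.716/0.814 = 12.0%
- week 72 to 96: 1 − 0.75^(24/52) = 12.4%

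Illustration: 100 patients are at risk at week 48, 12 stop before week 72 with no further sample, and 10% (assumed) have a first sustained low value. Then 8.8 of the remaining 88 are confirmed. The planned rule gives 8.8/100 = 8.8%; the correct figure is 8.8/88 = 10%. Early onsets lose little because the next visit is close; later onsets lose more.

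**Simulation.** 60,000 patients per scenario on the planned schedule, under three assumed patterns: persistently low from week 8, intermittent, and late onset. Planned rule: censor at end of treatment and exclude patients with fewer than two on-treatment results. Corrected rule: censor at the last on-treatment value with a next on-treatment value at least 21 days later. The early-stop sample, when taken, falls 17 days after the last injection. Cumulative confirmed incidence at end of treatment (%), planned / corrected:

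| Discontinuation, early-stop sample | Persistent | Intermittent | Late |
|---|---|---|---|
| None | 30.0 / 30.0 | 33.2 / 33.2 | 32.3 / 32.3 |
| 10%, 12.5%, taken | 29.6 / 29.8 | 32.8 / 33.1 | 32.1 / 32.4 |
| 10%, 12.5%, not taken | 29.9 / 30.1 | 32.9 / 33.7 | 31.0 / 32.2 |
| 20%, 25%, taken | 29.4 / 29.9 | 33.2 / 33.8 | 31.9 / 32.5 |
| 20%, 25%, not taken | 29.6 / 30.1 | 31.9 / 33.5 | 29.5 / 32.1 |

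At the planned dropout the shortfall is 0.5 to 0.6 points with the sample and 0.5 to 2.6 points without it. If the exclusion removed nobody, which bounds the effect of counting off-treatment results, the last row's planned figures become 29.2, 31.6 and 29.4, a shortfall of 0.9 to 2.7 points. A further simulation gave 0.4 to 0.6 points with the sample and 0.9 to 3.0 without. The corrected rule matches the true confirmed incidence within about 0.2 points throughout.

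**The case against.** The strongest reply is the early-stop visit. A reader might infer that anyone who stops between scheduled visits can never be confirmed. The protocol does not support that: the sample normally falls inside the 21-day tail, includes lipids, and counts. It removes most of the larger bias. What remains arises mainly when that sample comes within 21 days of the previous value, or is not obtained, since the protocol asks for the 5-day timing only if possible.

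Three other strong readings are tempting, and the documents do not support them:

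- *That the plan understates how many patients reach very low LDL-C.* The at-least-one and two-consecutive proportions are reported separately, and the censoring rule touches neither. Only the curve for confirmed events is affected.
- *That SAP 4.8 limits the curve to patients who have the event, so that it must reach 100%.* SAP 5.8 states how event-free patients are censored and names the safety population, so 4.8 is best read as defining the event time. This is loose wording.
- *That flatness after week 72 is a product of the censoring rule.* On scheduled visits, no later first value can be confirmed under either rule.

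It is also fair to say that the analysis is descriptive and has no bearing on the primary noninferiority conclusion. All of this stands and limits the point to a minor one.

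**Conclusion.** The mismatch between a confirmed event and end-of-treatment censoring is real, and its direction is clear: the curve for confirmed LDL-C below 25 or 15 mg/dL is biased slightly low when patients stop early. The exclusion of patients with fewer than two post-baseline results does not cure it. On about 30% confirmed, the shortfall is about 0.5 points if the early-stop sample is taken, up to about 3 points if it is not, and nil without early stopping.

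These sizes rest on assumed LDL-C patterns, on reading the sample-size dropout as treatment discontinuation, and on stopping being unrelated to LDL-C. The documents supply none of these. Minor priority.

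**What to change.** In SAP 5.8, for the confirmed-event curve only, censor event-free patients at their last on-treatment LDL-C that has a next on-treatment LDL-C at least 21 days later. Apply the exclusion on the same basis: drop patients with no such confirmable value, instead of those with fewer than two post-baseline results. Reword SAP 4.8 so that the analysis set is safety patients with a confirmable value, and note that on the planned schedule the curve carries no information after week 72.

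Censoring simply at the last-but-one on-treatment value is not enough. If the early-stop sample follows that value by less than 21 days, the value is itself unconfirmable and the patient is still counted at risk on its date.

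The cost is SAP wording, one derived variable and a slightly smaller risk set. No new data are needed.
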